**[name]**

## Background

The Efficacy and Safety of Cerebrolysin in the Treatment of Aphasia after Acute Ischemic Stroke (study code: ESCAS; protocol number: FSNN20200207) study is an exploratory, prospective, randomized-controlled, double-blinded Phase 4 clinical trial. The study aims to assess the efficacy and safety of Cerebrolysin in combination with speech therapy compared to a placebo (saline solution) in combination with speech therapy for the treatment of aphasia following acute ischemic stroke.

## Purpose of this SAP

The purpose of this Statistical Analysis Plan (SAP) is to provide a detailed and comprehensive plan for the statistical analyses that will be conducted on the data collected during the ESCAS study. The SAP ensures the transparency, consistency, and reproducibility of the study's data analysis, and helps avoid potential biases and data-driven decisions by prespecifying all planned analyses before data collection. This document will outline the statistical methods for analyzing the primary and secondary endpoints, as well as any exploratory endpoints, and will describe the approach for handling missing data, data transformations, and subgroup analyses.

By following this SAP, the study team can ensure that the results of the ESCAS study are analyzed and reported in a scientifically sound and rigorous manner, in accordance with best practices and regulatory guidelines. This will ultimately contribute to the assessment of the safety and efficacy of Cerebrolysin in the treatment of aphasia after acute ischemic stroke, and inform clinical decision-making and future research in this area.

## Objective

### Primary objectives

The primary objective of the ESCAS study is to assess the efficacy of Cerebrolysin and speech therapy versus placebo (saline solution) and speech therapy at 30, 60, and 90 days after baseline. Efficacy will be evaluated using the Western Aphasia Battery (Romanian translated version) scores at each time point. The primary outcome measure is the change in Western Aphasia Battery score from baseline to each follow-up time point (30, 60, and 90 days).

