### Assumptions considered in sample size calculations

The sample size calculation was based on the following assumptions:

- Type I error (alpha): The probability of finding a statistically significant treatment effect when there is none. In this study, an alpha level of  $\alpha=0.05$  was chosen, which is a commonly used threshold in clinical research.
- Type II error (beta): The probability of failing to detect a true treatment effect when one exists. In this study, a beta level of  $\beta=0.2$  was chosen, which corresponds to a statistical power of  $(1 - \beta)=0.8$ . This means that there is a  $(1 - \beta)$  probability of detecting a true effect, if present.
- Effect size (ES): The expected magnitude of the difference in treatment outcomes between the Cerebrolysin group and the placebo group. In this study, a medium effect size of ES was assumed, based on prior research and expert opinion.

Based on these assumptions, a power analysis was conducted to determine the necessary sample size for each treatment group. The analysis indicated that a sample size of N participants per group would be required to achieve the desired level of statistical power  $(1 - \beta)$  while maintaining an acceptable type I error rate ( $\alpha$ ).

Therefore, the ESCAS study will enroll a total of at least 2N participants, with at least N participants allocated to the Cerebrolysin group and at least N participants allocated to the placebo group. This sample size will ensure that the study has adequate power to detect a treatment effect of the expected magnitude while minimizing the risks of false positive and false negative results.

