## Assumed parameters and resulted sample size

Using G\*Power 3.1.9.7 and assuming a medium effect size  $d=0.5$ , an alpha error of  $\alpha=0.05$  and  $\beta=0.2$ , with an allocation ratio of 1 for Wilcoxon-Mann-Whitney test between two groups, we obtained a sample size of 53 patients per group. In order to provide a margin of error for situations such as patient withdrawal, SAEs or protocol violations, we have decided to recruit 120 patients in total for our study, 60 for each arm.

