## Primary endpoint

The primary endpoint of the ESCAS study is the comparison of the Western Aphasia Battery (Romanian translated version) scores between the Cerebrolysin and placebo groups at each time point (30, 60, and 90 days after study inclusion) compared to baseline. The Western Aphasia Battery is a standardized assessment tool used to evaluate language function in patients with aphasia. The study will use paired-measurement statistical tests to determine the efficacy of Cerebrolysin in improving language-related outcomes in the study population.

Additionally, unpaired-measurement statistical tests will be used to determine the differences between efficacy of the treatments between groups, at each time point.

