## Statistical analysis

For comparing numeric values of paired samples, differential values for each pair of values will be computed. Then, the distribution of those differentials will be compared with the normal distribution, using the Shapiro-Wilk test. If the differentials are normally distributed, we will use a one-sample Student T test (equivalent with the Student T test for paired samples) with null hypothesis  $\mu=0$ . If the differentials are not normally distributed, we will use a Wilcoxon signed-rank test with null hypothesis location=0.

For comparing numeric values of unpaired samples the normality of the values in each sample will be tested using Shapiro-Wilk test. If values from both samples are normally distributed, then variance equality between the samples will be assessed using the Bartlett test.

If the variances are equal, then the differences between the two samples will be assessed using a Student T test for unpaired samples and equal variances. If the variances are not equal, then a Student T test for unpaired samples and unequal variances will be used. In both cases, the null hypothesis will be that mean difference is equal to 0. If values from at least one of the samples are not normally distributed, then a Wilcoxon rank sum with null hypothesis of location difference equal to 0 will be performed.

For comparing ordinal values of paired samples, a Wilcoxon signed-rank test will be used, and for unpaired samples, a Wilcoxon rank-sum test will be used.

For comparing the difference in prevalences of variants of one dichotomous or nominal variable, among the groups of another dichotomous or nominal variable (i.e. testing the association between two dichotomous/nominal variables), the Chi test will be used or, where its assumptions would be violated (mainly due to small number of patients in any group), Fisher exact test will be used.

Where applicable, the two-tail p-value is reported. The type 1 error is assumed to be  $\alpha=0.05$ , and as such, results were considered statistically significant for  $p<0.05$ .

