### Confirmatory statistics

No confirmatory analysis planned.

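### Three visits are equally primary with no deciding visit or success rule, so the SAP's single 5% type I error and 80% power do not hold together

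*SAP*

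**What the plan says.** The SAP states its primary objective twice, under Objective and again under Study objectives, in the same terms: "The primary outcome measure is the change in Western Aphasia Battery score from baseline to each follow-up time point (30, 60, and 90 days". The Primary endpoint section adds that "unpaired-measurement statistical tests will be used to determine the differences between efficacy of the treatments between groups, at each time point". The Exploratory statistics section, the planned tables and the R function that builds the tables all follow this. Each gives one between-arm p-value at Visits 2, 3 and 4, and the set is produced for both the ITT and the PP population.

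On the threshold, the Statistical analysis section says "Where applicable, the two-tail p-value is reported", sets alpha at 0.05, "and as such, results were considered statistically significant for" p<0.05. This applies to every test alike. I found no deciding visit, no rule that any or all visits must succeed, no order of testing and no adjustment.

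The assumptions for the sample size define alpha at the level of the study: "The probability of finding a statistically significant treatment effect when there is none". Power is given as 0.8. The calculation itself takes d=0.5 and a 1:1 allocation "for Wilcoxon-Mann-Whitney test between two groups, we obtained a sample size of 53 patients per group"; 60 per arm are to be recruited. It covers one comparison, names no visit, and does not say whether the test is one- or two-sided.

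The SAP calls the trial exploratory, and under Confirmatory statistics it says "No confirmatory analysis planned".

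**The concern.** One alpha and one power describe one test. The SAP plans three and does not say how they combine into a verdict on the primary endpoint. The operating characteristics depend on that rule, and each possible rule departs from at least one of the two stated figures.

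There is also an interpretive risk. If one visit shows p<0.05 and the others do not, the SAP gives no basis for calling the primary endpoint met or not met, and the emphasis could settle on the favourable visit. The Data eligibility section allows corrections to the SAP after unblinding, so the rule needs to be fixed before then.

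**Working it through.** **Inputs from the SAP.** Three visits, two-tailed 0.05 at each, d=0.5, stated power 0.80, 53 per group calculated, 60 per arm recruited.

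**Assumptions.** The SAP gives no correlation between the visit-wise test statistics, so I take a common correlation r from 0.5 to 0.9. I take d=0.5 at every visit and normally distributed changes.

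**1. The SAP's own figure.** For the Wilcoxon-Mann-Whitney test with normal data, the effective size per group is m = n × 3/π. Power comes from the noncentral t with 2m − 2 degrees of freedom and noncentrality d × √(m/2).
- n=53: m = 50.6, noncentrality = 0.5 × √25.3 = 2.515. One-sided 0.05 gives power 80.3%, and 53 is the smallest n that reaches 80%. This matches the SAP exactly.
- Two-sided 0.05, as the analysis is planned: 70.2% at n=53. At n=60 (m = 57.3, noncentrality 2.676) it is 75.6%. The smallest n that reaches 80% is 67.

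So 53 is a one-sided figure, while the analysis is two-tailed.

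**2. Any visit counts, or all must.** Treat the three statistics as trivariate normal with common correlation r and critical value 1.96. Under the null the mean is 0. Under the alternative it is 2.676 (60 evaluable per arm).

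| r | Type I error, any visit | Power, any visit | Power, all visits |
|---|---|---|---|
| 0.5 | 12.5% | 93% | 56% |
| 0.6 | 11.8% | 92% | 58% |
| 0.7 | 10.9% | 90% | 61% |
| 0.8 | 9.8% | 87% | 64% |
| 0.9 | 8.4% | 84% | 68% |

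With independent visits the any-visit type I error would be 1 − 0.95³ = 14.3%. Under the all-visits rule type I error cannot exceed 5%. If there is no effect at any visit it is about 0.3% to 2.3% over the same range of r. At 53 evaluable per arm, all-visits power is 48% to 62%.

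**3. The three readings side by side, at 60 evaluable per arm.**

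| Rule | Type I error | Power |
|---|---|---|
| Any visit | 8.4% to 12.5% | 84% to 93% |
| All visits | at most 5% | 56% to 68% |
| One named visit | 5% | 76% |

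No row delivers 5% and 80% together.

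**4. What an adjustment would cost.** Bonferroni at 0.05/3 = 0.0167 per visit, two-sided, gives about 60% power at a given visit with 60 per arm, and needs 90 per arm for 80%.

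**The case against.** The strongest reply is that the trial is exploratory. The between-arm WAB tests sit under Exploratory statistics, no confirmatory analysis is planned, and the SAP nowhere promises control of error across the visits. Reporting each visit unadjusted is a common convention in that setting. This stands as a reason for lower weight. It does not remove the mismatch, because the same document names a primary outcome, presents alpha and power as properties of the study and declares results significant.

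A reader might infer that neither 5% nor 80% holds under any reading. The document does not support that. The 5% holds at each visit and is not exceeded if all visits must succeed. The 80% is reached at 60 evaluable per arm if any visit counts. Only the pair fails.

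A reader might also blame the three visits for the single-visit shortfall. That shortfall comes from sidedness and would remain with only one visit. It also depends on the data. At 60 per arm, two-sided, a t test on normal data has 77.5% power, and a Wilcoxon test on logistic data has 81%, although the logistic case does not reproduce 53. The SAP chooses between the two tests by a normality test, so 76% is not the exact power of the planned procedure.

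Finally, one might infer that an unfavourable visit could disappear. The pre-coded output puts all three visits in one table, so what remains is selective emphasis.

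**Conclusion.** The point holds for the two figures taken together. The SAP fixes three equally primary tests without a rule for combining them and attaches one alpha and one power to the whole. An any-visit rule raises type I error to roughly 1.7 to 2.5 times the stated 5% (8.4/5 to 12.5/5). An all-visits rule costs some 12 to 24 points of power against 80% (80 − 68 to 80 − 56).

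These sizes rest on assumed correlations of 0.5 to 0.9, the same d=0.5 at every visit, normal data and no losses from 60 per arm. The SAP intends the excess over 53 to absorb losses, so the 60-per-arm powers are the favourable end.

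Given the exploratory status, this should be corrected, but it does not undermine the trial.

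**What to change.** Before unblinding:

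1. In both Primary objectives sections and in Primary endpoint, name one between-arm comparison of WAB Aphasia Quotient change as primary, at two-sided 0.05. Day 90 (Visit 4) is the natural candidate. By the SAP's own schedule it is the only visit after all three treatment cycles, since the third runs over study days 57 to 70. The SAP does not rank the visits, so the choice is the sponsor's.
2. Make the other two visits supportive, or test them in fixed sequence after the primary one, each at 0.05 and only while the preceding test succeeds. This needs no split of alpha.
3. In the sample size section, state that 53 per group corresponds to a one-sided 0.05 test. Give the two-sided power for the named comparison as about 70% at 53 and 76% at 60 evaluable per arm (Wilcoxon, normal data). Naming a visit without this step would attach 80% power to a test that does not have it.

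The cost is a change of wording and a restated power, with no new data and no added enrolment. The downside is that significance at another visit alone could not be claimed as the primary result, and the stated power becomes less favourable.

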### Secondary objectives

The secondary objectives of the ESCAS study include the following:

- To assess the efficacy of Cerebrolysin and speech therapy versus placebo (saline solution) and speech therapy at 30, 60, and 90 days after baseline using measures of motor, neurological, and global functional outcome. These outcomes will be evaluated using the National Institutes of Health Stroke Scale (NIHSS), Barthel Index (BI), and modified Rankin Scale (mRS) scores at each time point.

- To evaluate the safety of Cerebrolysin and speech therapy versus placebo (saline solution) and speech therapy at 30, 60, and 90 days after baseline. Safety will be assessed by comparing the incidence of adverse events (AEs) and severe adverse events (SAEs) between the two treatment groups.
  - Additionally, we will measure specifically cardiovascular (such as, but not limited to stroke, myocardial infarction, atherosclerosis, vascular stenosis, as well as their recurrence), hematological (including anemia and vitamin B9 or B12 deficiency), renal system (including hyperuremia, hyperuricemia and urinary tract infections) and metabolic (including dyslipidemia, diabetes mellitus and atherosclerosis) related adverse events.

The secondary outcome measures include changes in NIHSS, BI, and mRS scores from baseline to each follow-up time point (30, 60, and 90 days), as well as the incidence of AEs and SAEs.

By addressing both the primary and secondary objectives, the ESCAS study will provide a comprehensive evaluation of the efficacy and safety of Cerebrolysin in the treatment of aphasia after acute ischemic stroke, in comparison with a placebo control group.

## Definitions and abbreviations

AE = adverse event

SAE = serious adverse event

CSP = clinical study protocol

SAP = statistical analysis plan

CSR = clinical study results

RDMNUM = randomization number of a patient, used as unique identifier of each trial participant across databases

NIHSS = National Institute of Health Stroke Scale / Score

WAB = Western Aphasia Battery

- WABSS = Western Aphasia Battery Spontaneous Speech
- WABC = Western Aphasia Battery Comprehension
- WABR = Western Aphasia Battery Repetition
- WABN = Western Aphasia Battery Naming
- WABAQ = Western Aphasia Battery Aphasia Quotient

mRS = Modified Rankin Scale

BI = Barthel Index

Abbreviations ending in T = in databases, signifies the total value of a score (used for NIHSS, WAB and its subscales, and BI)

Abbreviations starting with d = in databases, signifies a differential value of a score at a given visit, compared to visit 1 (used for NIHSS, WAB and its subscales)

Differential = usually a value computed as the difference between the values of a given score at two different visits

Statistician = person which is (part of the team) tasked with preparing the plan of the statistical analysis, preparing the data (including conversion to necessary formats), executing the statistical analysis and reporting the results

## Software utilized

We will use Microsoft Excel 2019, part of Microsoft Office 2019 suite (Microsoft Corporation, Redmond, WA), for data preparation and cleanup.

We will use R v. 4.3.1 (R Core Team, Vienna, Austria) and RStudio (Posit Software, PBC, Boston, MA) for data analysis. In the R workspace, we will load the following libraries:

stringr	Wickham H. stringr: Simple, Consistent Wrappers for Common String Operations [Internet]. 2022. Available from: https://CRAN.R-project.org/package=stringr
ggplot2	Wickham H. ggplot2: Elegant Graphics for Data Analysis [Internet]. Springer-Verlag New York; 2016. Available from: https://ggplot2.tidyverse.org
readxl	Wickham H, Bryan J. readxl: Read Excel Files [Internet]. 2023. Available from: https://CRAN.R-project.org/package=readxl
xlsx	Dragulescu A, Arendt C. xlsx: Read, Write, Format Excel 2007 and Excel 97/2000/XP/2003 Files [Internet]. 2020. Available from: https://CRAN.R-project.org/package=xlsx

Should additional libraries be required in processing of the data analysis, they will be mentioned and their use will be motivated in the CSR.

## Coding systems utilized

The original database uses the following variables which are of interest for the data analysis. In the following list, unless otherwise noted, x represents the moment of measurement (1=baseline, 4=last visit at 90 days after treatment). Note that for Barthel Index and modified Rankin Scale, only scores at visits 2, 3, and 4 (30, 60 and 90 days after baseline, respectively) are available, with no value at baseline.

- RDMNUM = randomization number (unique to each participant)
- 
- Western Aphasia Battery
  - WABAQ\_x = Aphasia Quotient (0-100%)
- NIH Stroke Scale (Score)
  - NIHSST\_x = total score (0-42)
- Barthel Index
  - BIT\_x = total score (0-100)
- Modified Rankin Scale

- MRS\_x = total score (0-6 where 0=no symptom and 6=dead)

AEs and SAEs were stored in a separate database, from which we will retrieve the following information:

- Randomization number
- Whether the AE represents a SAE or not
- Based on the nature of the AE, some will be further classified by a clinician as being of the following nature:
  - Neurological
  - Psychiatric
  - Cardiovascular
  - Renal
  - Hematological
  - Gastrointestinal
  - Metabolic
  - Respiratory
  - Immune-related
  - ENT
  - Ophthalmic

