#### Osteoarticular

For ease of data analysis, the statistician will convert the scores from the original database to a “long” format, with the following columns:

- RDMNUM
- Visit (1/2/3/4)
- is\_crb
- is\_PP
- WABAQ
- dWABAQ \*
- NIHSST
- dNIHSST \*
- BIT \*
- MRS \*

Columns starting with a *d* represent changes in scores at visits 2/3/4 compared to visit 1 (baseline). Columns marked with \* have values only for visit 2/3/4.

The column *is\_crb* will have a true/false value, depending on whether the patient was assigned to the treatment or placebo group. The column *is\_PP* will have a true/false value, depending on whether the specified data point will be analyzed as part of the *Per Protocol* analysis set. This is a mechanism through which the statistician or any other authorized person can exclude specific patients from each analysis set, depending on criteria such as protocol violations or patient withdrawal, and then prepare the subset for the statistical analysis routine. Assignment of each patient to the correct analysis sets is described later in this document.

AE-related data will be coded and analyzed in a separate database, with the following structure:

- RDMNUM
- SAE (is the AE a SAE?)

- AE\_total (the number of total AEs accused by the patient)
- SAE\_total (the number of total SAEs accused by the patient)
- Number of AEs accused by the patient, by category
  - AE\_cardiovascular
  - AE\_renal
  - ...

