### Secondary objectives

The secondary objectives of the ESCAS study include the following:

- To assess the efficacy of Cerebrolysin and speech therapy versus placebo (saline solution) and speech therapy at 30, 60, and 90 days after baseline using measures of motor, neurological, and global functional outcome. These outcomes will be evaluated using the National Institutes of Health Stroke Scale (NIHSS), Barthel Index (BI), and modified Rankin Scale (mRS) scores at each time point.
- To evaluate the safety of Cerebrolysin and speech therapy versus placebo (saline solution) and speech therapy at 30, 60, and 90 days after baseline. Safety will be assessed by comparing the incidence of adverse events (AEs) and severe adverse events (SAEs) between the two treatment groups.
  - Additionally, we will measure specifically neurological, psychiatric, cardiovascular, renal, hematological, gastrointestinal, metabolic, respiratory, immune-related, ENT, ophthalmic and osteoarticular related adverse events.

The secondary outcome measures include changes in NIHSS, BI, and mRS scores from baseline to each follow-up time point (30, 60, and 90 days), as well as the incidence of AEs and SAEs.

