## Treatment schedule

- Treatment Cycle 1 – 30 ml Cerebrolysin/saline and ST for 2 x 5 days (2 weeks)
  - Study days 1 – 14
  - 30ml Cerebrolysin/saline i.v.
  - 1h Speech Therapy
- Treatment Cycle 2 – 30 ml Cerebrolysin/saline and ST for 2 x 5 days (2 weeks)
  - Study days 29-42
  - 30ml Cerebrolysin/saline i.v.
  - 1h Speech Therapy
- Treatment Cycle 3 – 30 ml Cerebrolysin/saline and ST for 2 x 5 days (2 weeks)
  - Study days 57-70
  - 30ml Cerebrolysin/saline i.v.
  - 1h Speech Therapy

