## Planned tables and graphs

### Planned tables

- table1demographics.xlsx: demographics and baseline characteristics of each group; this table will also contain the results of the statistical tests done for comparability between groups
- 
- itt/3dWABAQ.xlsx: WAB Aphasia Quotient differentials at visits 2/3/4, comparisons with baseline and comparisons of differentials between groups, at each visit
- itt/4dNIHSST.xlsx: NIHSS differentials at visits 2/3/4, comparisons with baseline and comparisons of differentials between groups, at each visit
- itt/5BIT.xlsx: Barthel Index scores at visits 2/3/4, comparisons of differentials from visits 3/4 against visit 2, and comparisons of those differentials between groups, at visits 3/4
- itt/6MRS.xlsx: modified Rankin Score at visits 2/3/4, comparisons of differentials from visits 3/4 against visit 2, and comparisons of those differentials between groups, at visits 3/4
- pp/3dWABAQ.xlsx: WAB Aphasia Quotient differentials at visits 2/3/4, comparisons with baseline and comparisons of differentials between groups, at each visit
- pp/4dNIHSST.xlsx: NIHSS differentials at visits 2/3/4, comparisons with baseline and comparisons of differentials between groups, at each visit

- pp/5BIT.xlsx: Barthel Index scores at visits 2/3/4, comparisons of differentials from visits 3/4 against visit 2, and comparisons of those differentials between groups, at visits 3/4
- pp/6MRS.xlsx: modified Rankin Score at visits 2/3/4, comparisons of differentials from visits 3/4 against visit 2, and comparisons of those differentials between groups, at visits 3/4
- AE\_table.xlsx: counting of total AEs, SAEs and specific AE categories, as well as statistical tests between groups.

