# AE preprocessing ----
# NB: if the AE classification is not complete, i.e. there are still NAs, fill them with the following
command (pay attention to which columns you execute this on)
for(i in 11:22) db_advers[is.na(db_advers[,i]),i]<-0

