# AE information table -----
db_adver2<-db_assign
for(i in 1:nrow(db_adver2)){
  rdmnum<-db_adver2$RDMNUM[i]
  db_adver2[i,"AE_total"]<-sum(db_advers$RDMNUM==rdmnum)
```

```
db_adver2[i,"SAE_total"]<-sum(db_advers$RDMNUM==rdmnum&db_advers$SAE=="yes")
for(j in
c("neurological","psychiatric","cardiovascular","renal","hematological","gastrointestinal","metabol
ic","respiratory","immune.related.AE","ENT","ophthalmic","osteoarticular"))
  db_adver2[i,paste0("AE_",j)]<-
sum(db_advers$RDMNUM==rdmnum&db_advers[,paste0("is_",j)]==1)
}
tbl_out<-data.frame(
  AE_category=as.character(),
  sub=as.character(),
  Crb=as.character(),
  Plc=as.character(),
  pval=as.character(),
  test=as.character()
)
db_aelong<-data.frame(
  AE_category=as.character(),
  is_crb=as.logical(),
  no_patients=as.numeric(),
  no_aes=as.numeric(),
  percent_patients=as.numeric()
)
for(i in 7:20){
  rws<-nrow(tbl_out)
  tbl_out[rws+1,1]<-db_names[i,"short"]
  tbl_out[rws+1:5,2]<-c("Patients with AEs in group","Total number of AEs in group","Mean
number of AEs per patient","Median (Q1-Q3) number of AEs per patient","Max number of AEs
per patient")
  xc<-db_adver2[db_adver2$is_crb,db_names[i,"short"]]
  xp<-db_adver2[!db_adver2$is_crb,db_names[i,"short"]]
  tbl_out[rws+1,3]<-paste0(sum(xc!=0)," (",round(sum(xc!=0)/length(xc)*100,3),"%)")
  tbl_out[rws+1,4]<-paste0(sum(xp!=0)," (",round(sum(xp!=0)/length(xp)*100,3),"%)")
  x<-contingency.table.test(table(db_adver2$is_crb,db_adver2[,db_names[i,"short"]]!=0))
  tbl_out[rws+1,5]<-beautiful.p.value(x[["p_chosen"]])
  tbl_out[rws+1,6]<-x[["shorthand"]]
  tbl_out[rws+2,3]<-sum(xc)
  tbl_out[rws+2,4]<-sum(xp)
  tbl_out[rws+3,3]<-descr.numeric.meansd(xc)
  tbl_out[rws+3,4]<-descr.numeric.meansd(xp)
  tbl_out[rws+4,3]<-descr.numeric.median(xc)
  tbl_out[rws+4,4]<-descr.numeric.median(xp)
  tbl_out[rws+5,3]<-max(xc)
  tbl_out[rws+5,4]<-max(xp)
  x<-test.numeric.unpaired(xc,xp)
```

```

tbl_out[rws+3,5]<-beautiful.p.value(x$p.value)
tbl_out[rws+3,6]<-x$final.test
for(j in 1:max(xc, xp)){
  tbl_out[rws+5+j,2]<-paste0("Patient with ",j," AEs")
  tbl_out[rws+5+j,3]<-paste0(sum(xc==j)," (",round(sum(xc==j)/length(xc)*100,3),"%)")
  tbl_out[rws+5+j,4]<-paste0(sum(xp==j)," (",round(sum(xp==j)/length(xp)*100,3),"%)")
}
rws<-(i-7)*2
db_aelong[rws+1:2,1]<-db_names[i,"short"]
db_aelong[rws+1:2,2]<-c(T,F)
db_aelong[rws+1,3]<-sum(xc!=0)
db_aelong[rws+2,3]<-sum(xp!=0)
db_aelong[rws+1,4]<-sum(xc)
db_aelong[rws+2,4]<-sum(xp)

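### AEs assigned to none of the 12 classes appear only in the totals, and the number left unclassified in each arm is never shown

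*SAP*

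**What the plan says.** The SAP section *Coding systems utilized* describes AE classification as follows: "Based on the nature of the AE, some will be further classified by a clinician as being of the following nature". Eleven classes are listed there, and the twelfth, "Osteoarticular", follows directly after. There is no rule for which AEs are to be classified.

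Under *Study objectives*, the secondary objectives repeat the same twelve: "Additionally, we will measure specifically neurological, psychiatric, cardiovascular, renal, hematological, gastrointestinal, metabolic, respiratory, immune-related, ENT, ophthalmic and osteoarticular related adverse events". The earlier *Objective* section names only cardiovascular, hematological, renal and metabolic events.

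The planned AE table is described as "counting of total AEs, SAEs and specific AE categories, as well as statistical tests between groups". The three AE graphs use the same rows. No listing by event term and no count of unclassified events is planned.

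In the R code, the AE preprocessing step covers the case of an unfinished classification with "for(i in 11:22) db_advers[is.na(db_advers[,i]),i]<-0".

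Under *Safety*, the incidence of specific AE types is a safety endpoint, intended to show tolerability. Treatment in both arms is "30ml Cerebrolysin/saline i.v".

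**The concern.** Three features act together. Classification is partial by design, the class list has no residual category, and the code turns a blank flag into a negative one. An AE that the clinician does not place, or has not yet placed, drops out of every class row and leaves no trace there. Class incidences can then be too low, and by different amounts in the two arms, without the table showing it.

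The events most likely to be affected are non-serious ones with no obvious organ class: skin events, general events such as fever, and infusion-site events. These bear on tolerability, which the safety endpoint is meant to describe. Inside the AE total they are mixed with all other AEs, so an arm difference confined to them would be hard to see.

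**Working it through.** **1. Do the lists and the code agree?**
- *Coding systems utilized*: 11 + 1 = 12 classes.
- *Study objectives*, secondary objectives: 12 classes, the same ones.
- Class vector in the AE information table code: 12 classes.
- Flag columns 11 to 22: 22 - 11 + 1 = 12.
- Rows 7 to 20 of `db_names`: 20 - 7 + 1 = 14, which is the AE total, the SAE total and 12 classes.

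The plan's own structure of 14 rows, 12 of them classes, is reproduced. No skin, general, infusion-site or residual class appears in any list.

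**2. Where does an event end up?** The counting logic was re-run on three test events:

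| Event | AE total | SAE total | Class row |
|---|---|---|---|
| Non-serious, no class flag | 1 | 0 | none |
| Serious, no class flag | 1 | 1 | none |
| Flagged immune-related | 1 | 0 | Immune-related |

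The AE total counts every record for the patient and the SAE total every record marked serious, whether or not a class flag is set. A class row needs a flag equal to 1. Once blanks have been filled with 0, an event examined and found to fit no class cannot be told apart from one never examined.

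**3. Illustration of size.** Inputs from the SAP: 60 per arm (*Assumed parameters and resulted sample size*), two-sided p<0.05 (*Statistical analysis*), and the coded rule (uncorrected chi-square if all expected counts are at least 5, otherwise Fisher). Assumed, because the SAP gives no AE rates: the rate r of the unlisted type in each arm, and a background rate b of other AEs of 30%, 50% or 70%, equal in both arms and independent of the unlisted type.

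The any-AE rate in an arm is b + (1 - b) × r. For r = 10% vs 0% and b = 30%, this is 0.30 + 0.70 × 0.10 = 37% against 30%. For b = 70%, it is 0.70 + 0.30 × 0.10 = 73% against 70%. Power is the exact binomial sum over all pairs of counts that the rule declares significant.

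| Unlisted type, active vs placebo | Dedicated row | Any-AE row (b = 70% to 30%) |
|---|---|---|
| 10% vs 0% | 56% | 7-13% |
| 15% vs 2% | 72% | 8-18% |
| 10% vs 5% | 14% | 6-7% |
| 15% vs 5% | 44% | 7-13% |
| 20% vs 10% | 33% | 7-12% |

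This covers the comparison of patients with at least one AE. The code also compares AE counts per patient, which is not modelled here.

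**The case against.** A reader might infer that reactions to an intravenous product have no row at all and are visible only in the AE total. The SAP does not support that. An allergic or hypersensitivity reaction can be placed under Immune-related, and a reaction with organ symptoms under that organ. Any serious event also counts in the SAE total. How rash, fever or phlebitis would be assigned is not stated.

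The argument from the route is also limited. Both arms follow the same schedule, 3 cycles × 2 × 5 days = 30 infusions, so local infusion events are to be expected on placebo too. The rows with 0% or 2% on placebo suit a product-specific reaction better than an infusion-site event. With 5-10% on placebo, a dedicated row is itself weak.

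It can further be said that the long class list is used consistently, that the trial is exploratory with no confirmatory analysis, that the zero-fill is written as a contingency, and that AE coding is often left to the protocol, which is not at hand. These points lower the weight of the concern. They do not remove it: this SAP and its code fix the rows of the safety tables, and a dictionary in the protocol would not add a row. Nor does the contingency wording help, because when the fill is used its effect is invisible in the output.

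**Conclusion.** The point holds in a limited form. Non-serious AEs that the clinician assigns to none of the 12 classes appear only in the AE total, and unclassified serious AEs only in the AE and SAE totals. Incomplete classification is read as absence from the class, and its extent by arm is never reported.

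The structural part rests on the text and code alone. The size rests on assumed rates. In every scenario examined the dedicated row has more power than the any-AE row, but the gap runs from wide (72% against 8-18%) to narrow (14% against 6-7%), depending mainly on the placebo rate. These figures also assume that the whole excess falls into one row and that the row is tested. If new rows are only descriptive, as is reasonable, the benefit is that the events can be seen. This is a cheap improvement to the safety reporting, not a flaw in the efficacy analysis, and nothing suggests an intention to hide events.

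**What to change.** - **Classification.** In *Coding systems utilized*, state that every AE, not just some, will be classified by a blinded clinician before database closure.
- **Classes.** Add at least an other/unclassified class, and preferably skin and general/infusion-site classes, there and in the secondary objectives under *Study objectives*. Reconcile the shorter list in the earlier *Objective* section.
- **Check.** In the AE preprocessing code, test that every AE has at least one class before the blanks are filled. Keep the fill: an AE with one class still has blanks in its other flags, and without the fill those make the patient's class counts missing and stop the routine.
- **Hard-coded sizes.** Update `db_names`, the flag range 11:22, the class vector, the 7:20 loop, and the 1:14 factor and its labels in the AE graph code. If the last is missed, three new classes give 17 × 2 = 34 rows against 14 × 2 = 28 factor values, and the code stops with an error.

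The cost is one to three extra AE rows (14 becomes 15 to 17), which can be shown without tests so that no multiplicity is added, a few lines of code, and classification of the remaining AEs by the clinician already assigned. No new data are needed.
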